6.3.12 Overall Survival

Overall survival (OS) is defined as the time from the date of study enrollment until time of death from any cause.

6.3.13 Event-Free Survival

Event-free survival (EFS) is defined as the duration of time from the date of study enrollment until time of disease relapse, disease progression, alternative therapy for renal cell carcinoma given (such as radiation), or death, whichever occurs first

6.4 IMMUNE-RELATED RESPONSE CRITERIA (irRECIST)

Modified immune-related response criteria (irRECIST) will also be employed in this study. This new classification is based on the recent learning from clinical studies with cancer immunotherapies that even if some new lesions appear at the beginning of a treatment or if the total tumor burden does not increase substantially, tumor regressions or stabilizations might still occur later. For this trial, the concepts of the irRECIST are combined with RECIST 1.1. Please refer to [APPENDIX E](#) for further details.

6.4.1 Immune-related BOR (irBOR)

The duration of Immune-related best overall response is measured from the time measurement criteria are met for irCR or irPR (whichever is first recorded) until the first date that recurrent or progressive disease is objectively documented (taking as reference for progressive disease the smallest measurements recorded since the treatment started). irSD, not meeting criteria for irCR or irPR, in absence of irPD.

The duration of overall irCR is measured from the time measurement criteria are first met for irCR until the first date that progressive disease is objectively documented. Confirmation of assessment might be delayed up to 12 weeks to confirm PD to account for flare.

6.5 TOXICITY CRITERIA

The following adverse event management guidelines are intended to ensure the safety of each patient while on the study. The descriptions and grading scales found in the revised NCI Common Terminology Criteria for Adverse Events (CTCAE) version 5.0 will be utilized for AE reporting. All appropriate treatment areas should have access to a copy of the CTCAE version 5.0. A copy of the CTCAE version 5.0 can be downloaded from the CTEP web site

(http://ctep.cancer.gov/protocolDevelopment/electronic_applications/ctc.htm).

7 NIH REPORTING REQUIREMENTS/DATA AND SAFETY MONITORING PLAN

7.1 DEFINITIONS

Please refer to definitions provided in Policy 801: Reporting Research Events found [here](#).

7.2 OHSRP OFFICE OF COMPLIANCE AND TRAINING

7.2.1 Expedited Reporting

Please refer to the reporting requirements in Policy 801: Reporting Research Events and Policy 802 Non-Compliance Human Subjects Research found [here](#). **Note:** Only IND Safety Reports that meet the definition of an unanticipated problem will need to be reported per these policies.

7.2.2 IRB Requirements for PI Reporting at Continuing Review

Please refer to the reporting requirements in Policy 801: Reporting Research Events found [here](#).

7.2.3 NCI Clinical Director Reporting

Problems expeditiously reported to the OHSRP in iRIS will also be reported to the NCI Clinical Director. A separate submission is not necessary as reports in iRIS will be available to the Clinical Director.

In addition to those reports, all deaths that occur within 30 days after receiving a research intervention should be reported via email to the Clinical Director unless they are due to progressive disease.

To report these deaths, please send an email describing the circumstances of the death to [name] at [contact] within one business day of learning of the death.

7.3 NIH REQUIRED DATA AND SAFETY MONITORING PLAN

7.3.1 Principal Investigator/Research Team

The clinical research team will meet on a regular weekly basis when patients are being actively treated on the trial to discuss each patient. Decisions about dose level enrollment and dose escalation if applicable will be made based on the toxicity data from prior patients.

All data will be collected in a timely manner and reviewed by the principal investigator or a lead associate investigator. Events meeting requirements for expedited reporting as described in section [7.2.1](#) will be submitted within the appropriate timelines.

The principal investigator will review adverse event and response data on each patient to ensure safety and data accuracy. The principal investigator will personally conduct or supervise the investigation and provide appropriate delegation of responsibilities to other members of the research staff.

8 SPONSOR SAFETY REPORTING

8.1 DEFINITIONS

8.1.1 Adverse Event

Any untoward medical occurrence in a patient or clinical investigation subject administered a pharmaceutical product and which does not necessarily have a causal relationship with this treatment. An adverse event (AE) can therefore be any unfavorable and unintended sign (including

an abnormal laboratory finding), symptom, or disease temporally associated with the use of a medicinal (investigational) product, whether or not related to the medicinal (investigational) product (ICH E6 (R2))

8.1.2 Serious Adverse Event (SAE)

An adverse event or suspected adverse reaction is considered serious if in the view of the investigator or the sponsor, it results in any of the following:

- Death,
- A life-threatening adverse event (see section **8.1.3**)
- Inpatient hospitalization or prolongation of existing hospitalization
 - A hospitalization/admission that is pre-planned (i.e., elective or scheduled surgery arranged prior to the start of the study), a planned hospitalization for pre-existing condition, or a procedure required by the protocol, without a serious deterioration in health, is not considered a serious adverse event.
 - A hospitalization/admission that is solely driven by non-medical reasons (e.g., hospitalization for patient or subject convenience) is not considered a serious adverse event.
 - Emergency room visits or stays in observation units that do not result in admission to the hospital would not be considered a serious adverse event. The reason for seeking medical care should be evaluated for meeting one of the other serious criteria.
- Persistent or significant incapacity or substantial disruption of the ability to conduct normal life functions
- A congenital anomaly/birth defect.
- Important medical events that may not result in death, be life-threatening, or require hospitalization may be considered a serious adverse drug experience when, based upon appropriate medical judgment, they may jeopardize the patient or subject and may require medical or surgical intervention to prevent one of the outcomes listed in this definition.

8.1.3 Life Threatening

An adverse event or suspected adverse reactions is considered “life-threatening” if, in the view of either the investigator or sponsor, its occurrence places the patient or subject at immediate risk of death. It does not include an adverse event or suspected adverse reaction that, had it occurred in a more severe form, might have caused death. (21CFR312.32)

8.1.4 Severity

The severity of each Adverse Event will be assessed utilizing the CTCAE version 5.

8.1.5 Relationship to Study Procedure

All AEs will have their relationship to study product assessed using the terms: related or not related.

- Related – There is a reasonable possibility that the study product caused the adverse event. Reasonable possibility means that there is evidence to suggest a causal relationship between the study product and the adverse event.
- Not Related – There is not a reasonable possibility that the administration of the study product caused the event.

8.2 ASSESSMENT OF SAFETY EVENTS

AE information collected will include event description, date of onset, assessment of severity and relationship to study product and alternate etiology (if not related to study product), date of resolution of the event, seriousness and outcome. The assessment of severity and relationship to the study product will be done only by those with the training and authority to make a diagnosis and listed on the Form FDA 1572 as the site principal investigator or sub-investigator. AEs occurring during the collection and reporting period will be documented appropriately regardless of relationship. AEs will be followed through resolution.

SAEs will be:

- Assessed for severity and relationship to study product and alternate etiology (if not related to study product) by a licensed study physician listed on the Form FDA 1572 as the site principal investigator or sub-investigator.
- Recorded on the appropriate SAE report form, the medical record and captured in the clinical database.
- Followed through resolution by a licensed study physician listed on the Form FDA 1572 as the site principal investigator or sub-investigator.

For timeframe of recording adverse events, please refer to section **6.1**. All serious adverse events recorded from the time of first investigational product administration must be reported to the sponsor.

8.3 REPORTING OF SERIOUS ADVERSE EVENTS

Any AE that meets protocol-defined serious criteria or meets the definition of Adverse Event of Special Interest that require expedited reporting must be submitted immediately (within 24 hours of awareness) to OSRO Safety using the CCR SAE report form. Any exceptions to the expedited reporting requirements are found in section **8.4**.

All SAE reporting must include the elements described in section **8.2**

SAE reports will be submitted to the Center for Cancer Research (CCR) at: [contact] and to the CCR PI and study coordinator. CCR SAE report form and instructions can be found at:

<https://ccrod.cancer.gov/confluence/display/CCRCRO/Forms+and+Instructions>

Following the assessment of the SAE by OSRO, other supporting documentation of the event may be requested by the OSRO Safety and should be provided as soon as possible.

8.4 WAIVER OF EXPEDITED REPORTING TO CCR

As death due to disease progression is part of the study objectives, and captured as an endpoint in this study, it will not be reported in expedited manner to the sponsor. However, if there is evidence suggesting a causal relationship between the study drug and the event, report the event in an expedited manner according to section [8.3](#).

8.5 SAFETY REPORTING TO THE PHARMACEUTICAL COLLABORATORS

Reporting will be per the collaborative agreement.

8.5.1 CTEP

Copies of all IND Safety Reports submitted to the FDA should be forwarded electronically to [contact] (please provide protocol number in subject line).

8.6 REPORTING PREGNANCY

All required pregnancy reports/follow-up to OSRO will be submitted to: [contact] and to the CCR PI and study coordinator. Forms and instructions can be found here: <https://ccrod.cancer.gov/confluence/display/CCRCRO/Forms+and+Instructions>

8.6.1 Maternal exposure

If a patient becomes pregnant during the course of the study, the study treatment should be discontinued immediately, and the pregnancy reported to the Sponsor no later than 24 hours of when the Investigator becomes aware of it. The Investigator should notify the Sponsor no later than 24 hours of when the outcome of the Pregnancy become known.

Pregnancy itself is not regarded as an SAE. However, congenital abnormalities or birth defects and spontaneous miscarriages that meet serious criteria (section [8.1.2](#)) should be reported as SAEs.

The outcome of all pregnancies (spontaneous miscarriage, elective termination, ectopic pregnancy, normal birth, or congenital abnormality) should be followed up and documented.

8.6.2 Paternal exposure

Male patients should refrain from fathering a child or donating sperm during the study and for 30 days after the last dose of avelumab.

Pregnancy of the patient's partner is not considered to be an AE. However, the outcome of all pregnancies (spontaneous miscarriage, elective termination, ectopic pregnancy, normal birth, or congenital abnormality) occurring from the date of the first dose until 30 after the last dose should, if possible, be followed up and documented.

8.7 REGULATORY REPORTING FOR STUDIES CONDUCTED UNDER CCR-SPONSORED IND

Following notification from the investigator, CCR, the IND sponsor, will report any suspected adverse reaction that is both serious and unexpected. CCR will report an AE as a suspected adverse reaction only if there is evidence to suggest a causal relationship between the study product and the adverse event. CCR will notify FDA and all participating investigators (i.e., all investigators to whom the sponsor is providing drug under its INDs or under any investigator's IND) in an IND safety report of potential serious risks from clinical trials or any other source, as soon as possible, in accordance to 21 CFR Part 312.32.

All serious events will be reported to the FDA at least annually in a summary format.

9 CLINICAL MONITORING

As a sponsor for clinical trials, FDA regulations require the CCR to maintain a monitoring program. The CCR's program allows for confirmation of: study data, specifically data that could affect the interpretation of primary and secondary study endpoints; adherence to the protocol, regulations, ICH E6, and SOPs; and human subjects protection. This is done through independent verification of study data with source documentation focusing on:

- Informed consent process
- Eligibility confirmation
- Drug administration and accountability
- Adverse events monitoring
- Response assessment

The monitoring program also extends to multi-site research when the CCR is the coordinating center.

This trial will be monitored by personnel employed by a CCR contractor. Monitors are qualified by training and experience to monitor the progress of clinical trials. Personnel monitoring this study will not be affiliated in any way with the trial conduct.

10 STATISTICAL CONSIDERATIONS

10.1 STATISTICAL HYPOTHESES

10.1.1 Primary Endpoints

Overall Response (CR + PR) by irRECIST 1.1 criteria in patients who receive at least 1 cycle of therapy with the 4 mcg/kg dose of rhIL-15.

10.1.2 Secondary Endpoints

- Rate and severity of AEs, duration of response, progression-free survival and overall survival in patients who receive at least 1 cycle of therapy
- Changes in percentage and absolute number of peripheral blood lymphocyte subsets.
- Quantitation of ADCC performed *ex vivo* on PBMCs obtained from the patients before and during treatment.
- Characterization of changes in immune cell infiltrates of tumor deposits by immunohistochemical and molecular analysis of core biopsies obtained before and during treatment

10.2 SAMPLE SIZE DETERMINATION

The primary objective of this trial is to determine the efficacy of combination treatment of CIV rhIL-15 on days 1-5 and IV anti PDL-1 avelumab on day 8 and 22 of the 28-day cycle in patients with treatment refractory PD-L1+ ($\geq 5\%$) metastatic clear-cell renal carcinoma in terms of overall response. All patients must have failed or relapsed and have progressive disease after at least 2 prior therapies that include multityrosine kinase inhibitor like axitinib or sunitinib and an anti-PD1

or PD-L1 ICI therapy like nivolumab. The primary endpoint will be overall response (OR) per irRECIST 1.1 criteria.

A Simon two stage Simon Optimal Design will be used for the analysis of the primary endpoint of overall response rate. A minimum of 12 (3 in the 2mcg/kg safety run-in cohort (Cohort 1) and 9 evaluable in the first stage) and maximum of 25 patients will be enrolled in order to have 17 evaluable patients treated at the recommended phase 2 dose for the CIV rhIL-15 schedule at dose 4 mcg/kg/day. A maximum of 19 patients may be enrolled in the phase 2 part of this trial to compensate for inevaluable patients. The sample size for this trial is based on the plan for 3 to 6 patients treated in the 2 mcg/kg/day safety run-in cohort and to accurately assess target 25% response rate in the 4 mcg/kg dosing cohort with a power of 80% to determine the feasibility if this rate were true. The overall Type I error was set at 5% and power at 80% that assumes a null hypothesis success rate of 5% versus a treatment with a 25% response rate. Patients treated in the 2 mcg/kg/day safety cohort will not be included in the primary end point analysis but will be included in the safety cohort and be assessed for the secondary endpoints.

Stage 1 for the 4 mcg/kg dose level will consist of 9 evaluable patients to provide evidence of effectiveness and safety. If at least 1 of the 9 patients achieves a radiographic response (> 20% reduction in tumor volume) the study will be allowed to recruit the total sample size of 17 evaluable patients, otherwise it will be stopped for futility (Stage I boundary). The second stage of the design requires 3 or more of the 17 patients to have a positive response for the treatment to be considered worthy of further investigation. If the null hypothesis is true, there is a 63% chance of terminating after Stage I. If the probability of success is actually 0.25, there is a 92% chance that 1 or more patients will exhibit a 20% reduction in tumor volume at Stage I. Patients discontinued from the trial will not be replaced and counted in an "Intent to Treat" analysis as evaluable and treatment failures. At the end of the trial, we will report poor performance if the treatment is rejected at Stage I, not meeting the criteria of at least 1 success in 9 cases. If there is no success at Stage II (at most 2 responses in 17 patients), we will report a failure to reject the null hypothesis using the conditional probability of the added patients.

To ensure that this combination, which has not been administered to patients previously, and the dose levels chosen for CIV rhIL-15 are safe, 3 to 6 patients will be treated at the 2 mcg/kg/day dose level to confirm the absence of dose limiting toxicities. Once the safety of the 2 mcg/kg dose level is confirmed the first 3 or 6 patients treated at the intended phase II dose of 4 mcg/kg/day will be evaluated likewise for dose limiting toxicities. If unacceptable toxicity is observed in ≥ 2 of the first 3 or 6 patients treated at these dose levels, entry into the trial and all treatment will be halted to review the safety data to determine if the treatment plan should be altered or the study terminated. If DLT that halts the trial is not observed in these safety run-in cohorts, the trial will proceed to the efficacy assessment as specified above. The protocol will be amended to include information from the Safety Run-in cohorts prior to opening phase II.

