6.3.5 Evaluation of Target Lesions

Complete Response (CR): Disappearance of all target lesions. Any pathological lymph nodes (whether target or non-target) must have reduction in short axis to <10 mm.

Partial Response (PR): At least a 30% decrease in the sum of the diameters of target lesions, taking as reference the baseline sum diameters.

Progressive Disease (PD): At least a 20% increase in the sum of the diameters of target lesions, taking as reference the smallest sum on study (this includes the baseline sum if that is the smallest on study). In addition to the relative increase of 20%, the sum must also demonstrate an absolute increase of at least 5 mm. (Note: the appearance of one or more new lesions is also considered progressions).

Stable Disease (SD): Neither sufficient shrinkage to qualify for PR nor sufficient increase to qualify for PD, taking as reference the smallest sum diameters while on study.

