10.3.2 Evaluable for objective response

Only those patients who have measurable disease present at baseline and have received at least one cycle of therapy with 4mcg/kg dose of rhIL-15, will be assessed on an intent to treat basis. Patients who discontinue treatment or die and are not restaged will be considered to be non-responders and included in calculating the response rate. Patients will have their response classified according to the definitions stated above, Section **6.3**. (NOTE: Patients who exhibit objective disease progression prior to the end of Cycle 1 will also be considered evaluable).

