16.5 APPENDIX E: MODIFIED IMMUNE-RELATED RESPONSE CRITERIA (irRECIST)

This new classification is based on the recent learning from clinical studies with cancer immunotherapies that even if some new lesions appear at the beginning of a treatment or if the total tumor burden does not increase substantially, tumor regressions or stabilizations might still occur later. The irRC were created using bi-dimensional measurements (as previously widely used in the World Health Organization criteria). For this trial, the concepts of the irRC are combined with RECIST 1.1 to come up with the modified irRC.

For modified irRC, only target and measurable lesions are taken into account. In contrast to the RECIST 1.1 criteria, the modified irRC criteria (a) require confirmation of both progression and response by imaging at 6-8 weeks after initial imaging and (b) do not necessarily score the appearance of new lesions as progressive disease if the sum of lesion diameters of target lesions (minimum of 10 mm per lesion, maximum of 5 target lesions, maximum of 2 per organ) and measurable new lesions does not increase by $\geq 20\%$.

The same method of assessment and the same technique should be used to characterize each identified and reported target lesion(s) at baseline, during the trial, and at the end of trial visit. All measurements should be recorded in metric notation. The modified irRC based on RECIST 1.1 are displayed below.

Modified immune-related response criteria are defined as follows:

New measurable lesions: Incorporated into tumor burden.

New non-measurable lesions: Do not define progression but precludes (irCR).

Overall irCR: Complete disappearance of all lesions (whether measurable or not) and no new lesions. All measurable lymph nodes also must have a reduction in short axis to 10 mm.

Overall irPR: Sum of the longest diameters of target and new measurable lesions decreases $\geq 30\%$.

Overall irSD: Sum of the longest diameters of target and new measurable lesions neither irCR, irPR, (compared to baseline) or irPD (compared to nadir).

Overall irPD: Sum of the longest diameters of target and new measurable lesions increases $\geq 20\%$ (compared to nadir), confirmed by a repeat, consecutive observations at least 4 weeks (normally it should be done at 6 weeks) from the date first documented.

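### The Stage I futility gate is a 20% fall in tumor volume, but its stated 63% and 92% rest on rates given only for irRECIST CR/PR

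*Combined protocol and SAP*

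**What the plan says.** Section 10.2 says that a Simon optimal design "will be used for the analysis of the primary endpoint of overall response rate", with a null rate of 5%, a target of 25%, Type I error of 5% and power of 80%. Section 10.1.1 defines that endpoint as "Overall Response (CR + PR) by irRECIST 1.1 criteria in patients who receive at least 1 cycle of therapy" at the 4 mcg/kg dose. Section 10.3.2 adds: "Patients will have their response classified according to the definitions stated above", pointing to Section 6.3.

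Both printed definitions of partial response work on diameters. Section 6.3.5 has "At least a 30% decrease in the sum of the diameters of target lesions". Appendix E begins "Overall irPR: Sum of the longest diameters of target and new measurable lesions decreases" and sets the same 30% threshold. Section 6.3.1 requires confirmation at least 4 weeks later. Under Section 6.3.3, lesions are recorded by diameter and the diameters are summed.

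The Stage I rule in Section 10.2 names a different event: "If at least 1 of the 9 patients achieves a radiographic response (> 20% reduction in tumor volume". The same paragraph states a 63% chance of stopping under the null. For a true rate of 0.25 it says "there is a 92% chance that 1 or more patients will exhibit a 20% reduction in tumor volume at Stage I". The final rule asks for 3 or more of 17 and describes failure as "at most 2 responses in 17 patients". The précis and Section 3.1 make the same gate depend on clinical activity, which they do not define.

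**The concern.** The 5% and 25% behind the Stage I figures are given for overall response. The gate is a different and generally easier event, in a quantity the trial does not plan to measure, with no stated null or target rate. The figures therefore describe the gate only if it is read as CR/PR, and the text says otherwise twice.

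Stage I is the only efficacy stop with a numeric rule; Section 13.1 lists futility only as a general ground. If the gate is easier to pass than CR/PR, a regimen with a true 5% response rate goes on to 17 patients more often than the design promises. Shrinkage short of response is realistic: Section 1.2.10.1 reports no responses in the first-in-human rhIL-15 trial, yet 5 patients had decreases of 10% to 30% in marker lesions. That trial used another schedule without avelumab, so it supplies no rate here.

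**Working it through.** **Reproducing the plan.** Inputs from Section 10.2: p0 = 0.05, p1 = 0.25, stop at 0/9, fail at 2/17 or fewer.

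- Stop under the null: 0.95^9 = 0.630 (stated 63%).
- Pass Stage I at 25%: 1 − 0.75^9 = 0.925 (stated 92%).
- Type I error: P(X17 ≥ 3) − 0.95^9 × P(X8 ≥ 3) = 0.0503 − 0.6302 × 0.0058 = 0.0466.
- Power: 0.8363 − 0.0751 × 0.3215 = 0.812.
- Expected N under the null: 9 + 8 × (1 − 0.630) = 11.96.

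A search over designs up to n = 30 returns 0/9, 2/17 as the optimal one. The arithmetic is sound for CR/PR.

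**How far apart the two events are.** Under uniform shrinkage, a 20% volume fall is a diameter fall of 1 − 0.8^(1/3) = 7.2%, and a 30% diameter fall is a volume fall of 1 − 0.7^3 = 65.7%. If volume is read loosely as the diameter sum, a 20% fall is still stable disease under Section 6.3.5.

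The gate is not looser in every patient. Take spherical target lesions of 50, 15 and 15 mm and let the two small ones vanish. The diameter sum goes from 80 to 50 mm (−37.5%, a PR), but volume falls by only 1 − 50³/(50³ + 2 × 15³) = 5.1%.

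**Effect if every CR/PR meets the gate.** Let q be the null rate of the gate event (assumed; the plan gives none). The stopping chance is (1 − q)^9, expected N is 9 + 8 × [1 − (1 − q)^9] with no enrolment past the ninth patient before the look, and Type I error is 0.0503 − (1 − q)^9 × 0.0058.

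| q | Stop under null | Expected N | Type I error (3/17 counts CR/PR) |
|---|---|---|---|
| 5% (as designed) | 63% | 12.0 | 4.66% |
| 10% | 39% | 13.9 | 4.80% |
| 15% | 23% | 15.1 | 4.89% |
| 20% | 13% | 15.9 | 4.95% |

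Whatever the gate, Type I error cannot exceed P(X17 ≥ 3) at 5% = 5.03%.

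**Effect if some CR/PRs miss the gate.** Let a share c of CR/PRs and a share s of non-responders meet it (both assumed). The null gate rate is g = 0.05c + 0.95s and the stopping chance is (1 − g)^9. Power is P(X17 ≥ 3) minus the probability that X17 ≥ 3 but none of the first nine meets the gate, at p = 0.25.

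| s | c | Stop under null | Power |
|---|---|---|---|
| 0 | 0.9 | 66% | 0.795 |
| 0 | 0.8 | 69% | 0.771 |
| 5% | 0.9 | 42% | 0.810 |
| 5% | 0.8 | 44% | 0.793 |

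With s = 10% the stopping chance is 26% (c = 0.9) or 27% (c = 0.8). It drops below 63% once s exceeds 0.05(1 − c)/0.95, which is 0.5% at c = 0.9 and 1.1% at c = 0.8.

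**The case against.** The strongest reply is that this is a drafting slip whose intent can be recovered. Section 10.2 assigns the design to overall response, Section 10.1.1 defines that as CR plus PR, and the Stage I paragraph itself speaks of a radiographic response and of successes. The two probabilities are conditional on rates of 0.05 and 0.25, so they are right for any event with those rates. If volume was meant loosely as the diameter sum, the gap is 20% against 30%: essentially every PR then meets the gate, and the scenarios with missed CR/PRs fall away. The size of the effect rests on assumed rates throughout, and the final test is hardly touched.

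Most of this is fair. One event was probably intended, and the harm is confined mainly to the futility stop. But the parenthesis is the operative definition of that stop, the volume wording is repeated, and nothing elsewhere corrects it. The loose reading does not remove the conflict either, since a 20% diameter fall is not a PR and has no stated rate.

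**Conclusion.** The concern holds: the Stage I gate as written is not the event to which the plan assigns 5% and 25%, so 63% and 92% are justified only if the gate is CR/PR. If every CR/PR meets the gate, 63% is an upper limit on the null stopping chance. Without that assumption a lower stopping chance is likely but not guaranteed.

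The size cannot be fixed from the documents. At the assumed null gate rates of 10% to 20%, the cost is about 2 to 4 extra expected patients under the null, within the planned 17. Power does not fall below 0.812 if every CR/PR meets the gate; in the scenarios where 80% to 90% do and at most 5% of non-responders do, it is 0.77 to 0.81. The Type I bound of 5.03% assumes that the 3-of-17 rule counts CR/PR, which the plan implies but does not say in words. This should be fixed, but it does not threaten the primary conclusion on that reading.

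**What to change.** In Section 10.2, replace both volume phrases, and the undefined positive response in the 3-of-17 rule, with irRECIST CR or PR as defined for the primary endpoint. Use the same term for the gate in the précis and Section 3.1. State whether an unconfirmed response counts at the Stage I look. With one confirmed event at both stages, 63%, 92%, Type I error 0.047 and power 0.81 all hold. If unconfirmed responses count at the look, call 63% an upper bound: at an assumed unconfirmed null rate of 6%, 7% or 8% the stopping chance is 0.94^9 = 57%, 0.93^9 = 52% or 0.92^9 = 47%.

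If a lenient gate is wanted because responses may come late (Sections 6.3.2 and 6.4), define it on the diameters actually measured, give its null and target rates, and recompute the Stage I figures.

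The change is wording only, with no extra patients or scans, and Section 10.2 already plans an amendment before phase II opens. The drawback is a possible wait for a confirmatory scan. With 28-day cycles, scans after cycles 2 and 4 and a 4-week confirmation interval, that is about 8 + 4 = 12 or 16 + 4 = 20 weeks after the ninth patient starts, unless one of the nine has a response confirmed sooner. A lenient gate avoids some of that wait but needs rates the plan does not yet give.
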